#### Peak TNSS

The peak TNSS should be the highest TNSS value between 0 hour and hour 1 inclusive.

#### Total Ocular Symptom Score (TOSS)

TOSS (measured on a 0-3 scale, 3 being severe) is a composite symptom assessment of ocular symptoms (Itchy, Red, tearing [eyes watering], and swelling [puffy eyes]). The TOSS score will be recorded during the NAC assessments (Screening Visit 3 and Visit 16). The TOSS score will be recorded approximately every 10 minutes (up-titration symptom score), up until they reach the concentration of Timothy Grass extract that was used to achieve a TNSS  $\geq 7$  at their baseline NAC visit. This TOSS score will be recorded. The subject will be observed for the subsequent hour and the TOSS score will be recorded at 5 minutes, 15 minutes, 30 minutes, 45 minutes, 1 hour, and then hourly up to and at 6 hours.

#### Peak nasal inspiratory flow (PNIF)

Peak nasal inspiratory flow (measured in nasal patency, L/min) will be measured and recorded approximately every 10 minutes during the uptitration phase of the NAC and will be measured and recorded during the subsequent hour after peak TNSS is achieved (at 5 minutes, 15 minutes, 30 minutes, 45 minutes, and 1 hour) and hourly up to and at 6 hours. The PNIF will be performed at each NAC visit (Screening Visit 3 and Visit 16).

#### Sneeze Count

Sneezes will be counted and recorded approximately every 10 minutes during the uptitration phase of the NAC and will be measured and recorded during the subsequent hour after peak TNSS is achieved (at 5 minutes, 15 minutes, 30 minutes, 45 minutes, and 1 hour) and hourly up

to and at 6 hours as noted. The sneezes count will be performed at each NAC visit (Screening Visit 3 and Visit 16).

#### Skin Prick Test (SPT) with Serial Allergen Titration

The SPT with serial allergen titration assesses the early phase reaction at 0-60 minutes. The skin prick test with serial allergen titration procedure will be performed two times during the study: at visit 3 (on the day of the screening NAC) and at the EOT NAC visit (visit16). The procedure should be performed over a 30 minute time period (15 min placement of skin pricks, 15 minutes (+/- 2 minutes) after placement to evaluate responses) during the last 2 hours of the NAC day when the subject is otherwise undergoing hourly assessments.

The test will be performed in duplicate by titration of Timothy grass extract at six doses ranging from 14-10000 BAU. Duplicate probes with a negative control solution and a positive histamine control will be administered simultaneously with Timothy grass extract probes. A mean wheal diameter 3 mm greater than the negative control is considered a positive test result. Skin responses to the skin prick test with serial allergen titration will be measured 15 minutes after placement (+/- 2 minutes). Mean wheal diameters will be calculated by adding the longest diameter to the longest orthogonal diameter and dividing by 2. For each of the duplicate skin prick tests, the longest and longest orthogonal diameters should be recorded, and the mean diameter of each wheal calculated to two decimal places. The mean wheal diameters from the duplicate skin pricks will then be averaged and recorded.

The formula used to calculate the average wheal diameter AUC over allergen concentrations is similar as the one inside Section 6.2, where  $t_i$  is  $c_i$ , the concentration (in BAU/ml) for which  $D_i$  is measured.  $D_i$  is the average wheal diameter obtained at concentration  $c_i$ ,  $c_0 = 14$ ,  $c_1 = 41$ ,  $c_2 = 123$ ,  $c_3 = 370$ ,  $c_4 = 1111$ ,  $c_5 = 3333$ ,  $c_6 = 10000$ . The formula used to calculate the average wheal diameter AUC over log-transformed allergen concentrations is similar to above, however,  $c_i$  is the log-transformed concentration.

The change from baseline, percent change from baseline values for the mean wheal diameters from measurement 1 and 2 for skin prick test of negative control, positive histamine control, and each concentration level of Timothy grass allergen will be also summarized.

#### Intradermal Allergen Injection

The intradermal allergen injection assesses late phase reaction from 6-24 hours. The intradermal allergen injection procedure will be performed two times during the study: at visit 3 (on the day of the screening NAC) and at the EOT NAC visit (visit16). The intradermal allergen injection procedure will be performed on the extensor and volar aspect of the forearm. The intradermal allergen injection will be performed at the beginning of the NAC day, before the NAC begins, as described below. The skin response to the intradermal allergen will be evaluated at approximately 6 hours after placement- at the end of the NAC day. The mean wheal diameter measured at 15 minutes and 6 hours after injection for the Timothy grass allergen extract of 14, 41, 123 BAU/ml will be collected.

The maximum mean wheal diameters 6 hours after injection at the EOT NAC visit (visit 16) versus the maximum mean wheal diameters 6 hours after injection at the screening NAC visit (Visit 3) up to the largest concentration level at EOT NAC visit will be identified. The change and percent change between these two values will be calculated and summarized. If the

maximum mean wheal diameters are not at the same Timothy grass allergen concentration at Visit 3 and EOT/Visit 16, the assessment at the smaller one of the two concentrations will be used in the change and percent change analysis. That is, the wheal diameters of Visit 3 and EOT/Visit 16 for the change and percent change calculation should be based on the same concentration.

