### **3.2.8.3. Skin: Early-Phase (0–60 min) and Late-Phase (6 hr) Skin Reaction to Allergen Challenge**

The SPT with serial allergen titration assesses the early phase reaction (EPR) at 0-60 min. The intradermal allergen injection will be performed to assess late phase reaction (LPR) at 6 hours. The early phase reaction is characterized by histamine release and is thought to reflect cutaneous mast cell degranulation upon allergen exposure. The allergen-induced cutaneous LPR is characterized by an influx of inflammatory cells, including basophils, eosinophils, activated CD4+-cells, and neutrophils which arrive at the site of inflammation some hours after provocation.

Allergen specific immunotherapy with Timothy Grass has been shown to decrease both the early phase reaction after SPT, and late phase reaction after intra-dermal allergen challenge, as measured by the decrease of wheal size post challenge (Scadding, 2015b). In addition, short term grass SCIT treatment (13 weeks) led to significant and lasting reduction of LPR with statistical significance 12 months after the end of SCIT (Chaker, 2015a) (Chaker, 2015b). We hypothesize that dupilumab as an adjunct to SCIT treatment may further reduce skin allergic response to Timothy Grass and can further decrease LPR compared to SCIT alone. Based on expected reduction of IgE levels 12 weeks after dupilumab treatment in past AD studies, a reduction in mast cell activation may result in reduction in EPR and therefore reduced wheal sizes may also be expected.

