**4.2.3. Exploratory Endpoints**

- Change and percent change from baseline in the peak TNSS at week 17 for dupilumab + SCIT as compared to SCIT monotherapy and for dupilumab monotherapy as compared to placebo
- Change and percent change from baseline in TOSS AUC post NAC over the first hour of the challenge (0-1 hr post peak TNSS) at week 17 for dupilumab + SCIT as compared to SCIT monotherapy and for dupilumab monotherapy as compared to placebo
- Change and percent change from baseline (last pretreatment measurement) to week 17 in Skin Prick Test with Serial Allergen Titration, as measured by AUC of the wheal sizes (diameter) over the course of 0 hour to hour 1 after the challenge (early phase reaction)
- Change and percent change from baseline (last pretreatment measurement) to week 17 in the wheal size (diameter) induced by skin Timothy Grass intradermal injection 6 hrs after the challenge (late phase reaction)
- Change and percent change from baseline (last pretreatment measurement) to week 17 in PNIF AUC over the course of 0 hour to hour 1 and hour 1 to hour 6 after the challenge (early and late phase reaction)

- Change and percent change from baseline (last pretreatment measurement) to week 17 in sneeze count AUC over the course of 0 hour to hour 1 and hour 1 to hour 6 after the challenge (early and late phase reaction)
- Change and percent change from baseline (last pretreatment measurement) to week 17 in serum TARC
- Change and percent change from baseline (last pretreatment measurement) to week 17 in serum total IgE

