#### **5.7.2. Analyses of Secondary and Exploratory Efficacy Variables**

The change and percent change from baseline in continuous secondary and exploratory efficacy endpoints will be analyzed using the same approach as that used for the analysis of the primary endpoint, unless specified otherwise.

The biomarker related continuous endpoint will be analyzed using a rank based ANCOVA model with treatment and relevant baseline as covariates. Post-baseline LOCF method will be used to impute the missing data. The comparison will be performed between dupilumab +SCIT vs SCIT.

The proportion of subjects who achieve SCIT maintenance dose (4000 BAU) during 16 weeks of treatment will be compared by Chi-square test between dupilumab + SCIT and placebo for dupilumab +SCIT groups. The maximal tolerated SCIT dose during 16 weeks of treatment and the local skin wheal size at approximately 15 minutes after each SCIT injection during 16 weeks of treatment will be summarized descriptively. If the wheel size is too small to measure after the SCIT injection, the diameter is set to zero.

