## 10. APPENDIX

### 10.1. Summary of Statistical Analyses

#### Efficacy Analysis:

Parameter(s)	Endpoints	Primary Statistical Method	Supportive/Sensitivity Statistical Method	Subgroup Analysis
TNSS	percent change and absolute change from baseline in AUC for TNSS (0-1 hr post peak TNSS) at week 17	ANCOVA model, missing data imputed by Multiple Imputation (MI)	Yes	Yes
TOSS	percent change and absolute change from baseline in AUC for TOSS (0-1 hr post peak TNSS) at week 17	ANCOVA model, missing data imputed by Multiple Imputation (MI)	No	No
Skin Prick Test with Serial Allergen Titration	percent change and absolute change from baseline in AUC for wheal sizes (diameter) (0-1 hr post peak TNSS) at week 17	ANCOVA model, missing data imputed by Multiple Imputation (MI)	No	No
skin Timothy Grass intradermal injection	percent change and absolute change from baseline in wheal size (diameter) induced by skin Timothy Grass intradermal injection 6 hrs after the challenge) at week 17	ANCOVA model, missing data imputed by Multiple Imputation (MI)	No	No

Parameter(s)	Endpoints	Primary Statistical Method	Supportive/Sensitivity Statistical Method	Subgroup Analysis
PNIF	percent change and absolute change from baseline in PNIF AUC (0-1 hr post peak TNSS, and 1-6hr post peak TNSS) at week 17	ANCOVA model, missing data imputed by Multiple Imputation (MI)	No	No
sneeze count	percent change and absolute change from baseline in sneeze count AUC (0-1 hr post peak TNSS, and 1-6hr post peak TNSS) at week 17	ANCOVA model, missing data imputed by Multiple Imputation (MI)	No	No

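### The intradermal late-phase rule lets the week 17 wheals help choose the concentration at which change is read, which usually attenuates the difference between arms

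*SAP*

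**What the plan says.** Protocol 4.2.3 lists, as exploratory, the change and percent change to week 17 in "the wheal size (diameter) induced by skin Timothy Grass intradermal injection 6 hrs after the challenge (late phase reaction". It names no concentration.

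SAP 4.5.3 (Intradermal Allergen Injection) supplies the rule:

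- Mean wheal diameter at 15 minutes and 6 hours "for the Timothy grass allergen extract of 14, 41, 123 BAU/ml will be collected".
- The largest 6-hour wheal is found at Visit 16 and at Visit 3, the Visit 3 search running "up to the largest concentration level at EOT NAC visit will be identified".
- If the two maxima fall at different concentrations, "the assessment at the smaller one of the two concentrations will be used in the change and percent change analysis".
- The stated aim is that "the wheal diameters of Visit 3 and EOT/Visit 16 for the change and percent change calculation should be based on the same concentration".

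SAP 5.7.2 and the table in SAP 10.1 analyse the result as the primary endpoint is analysed: ANCOVA with treatment and baseline, after multiple imputation. The SAP gives no rule for ties or all-zero wheals in this test. Its only zero rule, in 5.7.2, concerns the wheal at the immunotherapy injection site: if that is too small to measure "after the SCIT injection, the diameter is set to zero". SAP 1.2.4 does not list the concentration rule among the modifications to the protocol.

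**The concern.** The expected effect is a smaller late-phase reaction: Protocol 3.2.8.3 hypothesises that dupilumab added to SCIT "can further decrease LPR compared to SCIT alone". The measuring point should therefore not depend on how far the reaction was suppressed. Here it can. Because the smaller concentration always wins, a Visit 16 maximum that moves down takes the comparison with it, while one that moves up has no effect. If treatment flattens the response so that the Visit 16 maximum drifts to 41 or 14 BAU/ml, the large Visit 3 wheal at 123 BAU/ml leaves the calculation.

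The drift is likelier in the more effective arm, so the arms can end up measured at different concentrations because of treatment. If the baseline covariate is the Visit 3 value at the chosen concentration, the ANCOVA also adjusts for something treatment has altered. At stake is a false or weakened null on the trial's skin late-phase measure, which is tested between arms at 5% and is reused in the biomarker correlations of SAP 5.12.

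**Working it through.** **Inputs.** The three concentrations, the 6-hour reading, the rule and the expected direction come from the documents. They give no wheal sizes, variability, detection limit or effect size for this test, and no power figure to reproduce. Every mm value below is an assumption.

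**Formula.** Let b and e be the Visit 3 and Visit 16 wheals at each concentration. Then c = the smaller of (concentration of the largest b, concentration of the largest e), and change = e at c minus b at c. All three concentrations are taken as given at both visits, so the cap on the Visit 3 search is treated as not binding.

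**Hand cases** (mm at 14/41/123 BAU/ml):

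| Visit 3 | Visit 16 | Read at | Rule | At 123 |
|---|---|---|---|---|
| 10/20/35 | 5/10/17.5 | 123 | −17.5 | −17.5 |
| 10/20/35 | 1/2/3.5 | 123 | −31.5 | −31.5 |
| 10/20/35 | 8/14/12 | 41 | 14 − 20 = −6 | 12 − 35 = −23 |
| 10/20/35 | 8/7/6 | 14 | 8 − 10 = −2 | 6 − 35 = −29 |
| 10/20/35 | 0/0/0 | 14 or 123, by tie rule | −10 or −35 | −35 |
| 10/30/28 | 5/12/15 | 41 | 12 − 30 = −18 | 15 − 28 = −13 |

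A clean proportional fall loses nothing. A Visit 16 maximum that moves down loses much. The last row shows an overstatement, with the Visit 3 maximum deciding.

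**Mean change with noise** (simulation, 200,000 subjects per scenario, proportional effect; loss = 1 − rule/fixed):

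| Visit 3 means, noise SD | True reduction | Fixed 123 | Rule | Loss |
|---|---|---|---|---|
| 10/20/35, 3 mm | 50 / 75 / 90% | −17.5 / −26.2 / −31.3 | −16.8 / −22.0 / −21.1 | 4 / 16 / 33% |
| 10/20/35, 6 mm | 50 / 75 / 90% | −17.5 / −26.1 / −30.4 | −13.2 / −16.2 / −16.2 | 25 / 38 / 47% |
| 20/25/30, 3 mm | 50 / 75 / 90% | −15.0 / −22.5 / −26.8 | −12.7 / −18.1 / −20.9 | 15 / 20 / 22% |

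If every wheal instead falls by the same number of mm, there is almost no loss until wheals reach zero. For 20/25/30 mm with noise SD 6 mm and a 15 mm fall, the rule gives −14.9 mm against −15.0 mm.

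**Between-arm effect, 25% versus 75% reduction.** d = difference in mean change / pooled SD of change.

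- 4/8/12 mm, between-subject SD 4, error SD 3, wheals under 3 mm recorded as 0: d is about 1.25 at fixed 123. Under the rule it is 0.46 with ties to the lowest concentration and 0.75 with ties to the highest.
- The other two curves, with between-subject SD 5 and error SD 3. Variance of change at fixed 123 is 2 × 3² + (0.25 × 5)² = 19.6 in one arm and 2 × 3² + (0.75 × 5)² = 32.1 in the other, so the pooled SD is √((19.6 + 32.1)/2) = 5.08.
  - 10/20/35 mm: 0.5 × 35 / 5.08 = 3.4 fixed; simulated rule about 1.9.
  - 20/25/30 mm: 0.5 × 30 / 5.08 = 3.0 fixed; simulated rule about 2.0.

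**Baseline used by the rule** (4/8/12 mm, ties to lowest). The mean Visit 3 value at the chosen concentration is 10.9 mm in the 25% arm and 8.3 mm in the 75% arm, although the arms start identical. That value is exactly zero, leaving percent change undefined, in 9% versus 23% of subjects (6% versus 9% with ties to the highest).

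**Alternatives on the same inputs.** Reading at the Visit 3 maximum concentration, or averaging over the three concentrations, each gives d = 1.23.

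**The case against.** The rule has a legitimate aim: both visits should be read at the same concentration. It uses both visits, so Visit 3 decides whenever its maximum is lower. The cap could also be read innocently, as restricting the Visit 3 search to concentrations actually injected at Visit 16; the wording allows either that or the concentration of the Visit 16 maximum. The inputs are assumed, the loss can be as small as 4%, and the endpoint is exploratory with no alpha assigned. All of this stands. It limits the size and consequence of the problem but does not remove the dependence on a post-randomisation result, and like-for-like reading is available without it.

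A reader might infer something stronger: that the concentration is set by the post-treatment result alone, and that the better the treatment works, the smaller the measured change. Neither holds. For 4/8/12 mm with ties to the lowest concentration, true reductions of 0/25/50/75/100% give mean changes of 0/−2.0/−3.6/−4.3/−4.2 mm. The measured fall grows up to 75% and slips only at complete suppression. With ties to the highest it keeps growing, from −6.3 mm at 75% to −8.9 mm at 100%. A reversal needs near-complete suppression and depends on the wheal curve and on a tie rule that the SAP does not state. Nor is the bias always towards no effect, as the 10/30/28 mm case shows.

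**Conclusion.** The concern holds as a rule that usually attenuates the effect, not one that inverts it. The Visit 16 result helps choose where the baseline is read, and nothing elsewhere in either document corrects this. Under a proportional effect with noise, the mean change is understated by 4–25% at a true 50% reduction and 22–47% at 90% on the two larger assumed curves. On the three curves tried, the rule keeps between roughly 37% (0.46/1.25) and 67% (2.0/3.0) of the standardised effect at fixed 123 BAU/ml. These sizes rest wholly on assumed wheals and spreads. The direction rests on a roughly proportional effect, or on stronger suppression at the higher concentrations; an equal-mm reduction would do little harm.

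Two gaps do not depend on the simulation: ties and all-zero wheals are undefined for this test, and the baseline value used can be changed by treatment. Primary and secondary results are untouched. The reach is this exploratory endpoint and the SAP 5.12 correlations that use it.

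**What to change.** Delete the smaller-concentration sentence in SAP 4.5.3 and define a like-for-like comparison that does not use the Visit 16 response.

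- **Preferred:** the mean, or log-concentration AUC, of the 6-hour wheal over all concentrations tested at both visits. SAP 4.5.3 already summarises the skin prick test over all concentrations by AUC. This also removes the tie problem.
- **Alternative:** read both visits at the concentration with the largest Visit 3 wheal, with a stated tie rule. Choosing a maximum at Visit 3 adds some regression to the mean, but the choice precedes treatment, so this is equal across arms.

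With either option, reword the cap so that it refers only to concentrations injected at both visits, state how an unmeasurable intradermal wheal is recorded, say what happens to percent change when baseline is zero, and name the baseline covariate.

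The cost is a small SAP edit and a short program change; the readings are already collected.

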## 4.6. Safety Variables

### 4.6.1. Adverse Events and Serious Adverse Events

Adverse events and serious adverse events will be collected from the time of informed consent signature and then at each visit until the end of the study, with the exception of symptoms that occur in response to the NAC on the day of the NAC. Allergic symptoms that occur in response to the NAC are not to be reported as AEs, as they will be recorded as outcome measures. However, AEs that occur in response to the NAC that are outside of expected symptoms which are recorded in response to the NAC, and/or SAEs, should be reported as AEs and SAEs.

All adverse events are to be coded to a “Preferred Term (PT)”, “High Level Term (HLT)” and associated primary “System Organ Class (SOC)” according to the Medical Dictionary for Regulatory Activities (MedDRA, latest version).

An **Adverse Event** is any untoward medical occurrence in a patient administered a study drug which may or may not have a causal relationship with the study drug. Therefore, an AE is any unfavorable and unintended sign (including abnormal laboratory finding), symptom, or disease which is temporally associated with the use of a study drug, whether or not considered related to the study drug.

AEs also include: any worsening (i.e., any clinically significant change in frequency and/or intensity) of a pre-existing condition that is temporally associated with the use of the study drug; abnormal laboratory findings considered by the investigator to be clinically significant; and any untoward medical occurrence.

A **Serious Adverse Event** is any untoward medical occurrence that at any dose results in death; is life-threatening; requires in-patient hospitalization or prolongation of existing hospitalization; results in persistent or significant disability/ incapacity; is a congenital anomaly/ birth defect; or is an important medical event.

The criteria for determining whether an abnormal laboratory, vital sign or ECG finding should be reported as an AE are as follows:

- Test result is associated with accompanying symptoms, and/or
- Test result requires additional diagnostic testing or medical/surgical intervention, and/or
- Test result leads to a change in dosing (outside of protocol-stipulated dose adjustments) or discontinuation from the study, significant additional concomitant drug treatment, or other therapy

The pre-treatment period is defined as the period from the patient providing informed consent up to the first dose of study drug. The pre-treatment AEs are AEs that developed or worsened in severity during pre-treatment period.

The treatment emergent period is defined as the period from the administration of first study dose to the EOS visit. The treatment-emergent period consists of the treatment period and follow-up period. The definitions of the treatment period and the follow-up period are described inside Section 3.3. Treatment-emergent AEs (TEAEs) are AEs that developed or worsened in severity compared to the baseline during the treatment emergent period. As only the worsening pre-existing AEs and new AEs reported during the treatment and follow-up period will be collected in the study, all AEs collected during the treatment and follow-up period are considered as TEAEs.

#### **4.6.2. Adverse Events of Special Interest**

In this study, the adverse event of special interest (AESI) category includes:

- Anaphylactic reactions
- Systemic or severe hypersensitivity reactions
- Malignancy (except in situ carcinoma of the cervix, non-metastatic squamous or basal cell carcinoma of the skin)
- Helminthic infections
- Suicide-related events
- Any type of conjunctivitis or blepharitis (severe or serious)
- Keratitis (any event regardless of severity or seriousness)

Section 10.4 provides a list of AESIs search criteria.

